## 9.5 Criteria for Defining the Severity of an Adverse Event

Adverse events, including abnormal clinical laboratory values, will be assessed according to the criteria below and entered in the eCRF:

Grade	Severity Assessment Standard
1-Mild	Events require minimal or no treatment and do not interfere with the subject's daily activities.
2-Moderate	Events result in a low level of inconvenience or concern with the therapeutic measures. Moderate events may cause some interference with functioning.
3-Severe	Events interrupt a subject's usual daily activity and may require systemic drug therapy or other treatment. Severe events are usually incapacitating.
4-Life-threatening	Any adverse event that places the subject or participant, in the view of the investigator, at immediate risk of death from the reaction as it occurred, i.e., it does not include a reaction that, had it occurred in a more severe form, might have caused death.
5-Death	Death related to AE.

## 9.6 Reporting of Adverse Events

At each evaluation, the subject will be questioned in a general way and no specific symptoms will be suggested. If any AEs have occurred, they will be recorded on the AE pages of the eCRF and in the subject's medical record. If known, the diagnosis should be recorded in preference to the listing of individual signs and symptoms.

During the Screening period (Day -45 to Day 0 prior to implantation), only SAEs related to study procedures will be reported beginning at the time the subject signs the informed consent form. From Day 0 after implantation to 1 year post-implantation (Month 12 visit) or ET visit, whichever occurs earlier, all AEs will be reported.

During the long-term follow-up period from 1 year to 3 years post-implantation, only the following will be reported by the investigator:

- All related SAEs
- All Events of Special Interest (as defined in [Section 9.3](#)).

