- 15 deaths, all after abandonment or during follow-up; none of the deaths were considered related to the presence of the HAV

Patency data for the 2 studies in dialysis access has been pooled for a combined Kaplan-Meier (K-M) analysis ([Lawson, 2016](#)). Based on these K-M plots the patency at 6, 12 and 24 months is estimated to be 60%, 26% and 15% (primary patency) and 97%, 91% and 77% (secondary patency).

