### 9.6.1 Reporting of Serious Adverse Events

Any SAE (as defined in [Section 9.2](#)) which occurs from Day 0 after implantation to 1 year post-implantation (Month 12 visit) or ET visit, whichever occurs earlier, whether or not causally related to the IMP, must be reported by the investigator to Humacyte or designee immediately (**no later than 24 hours after learning of its occurrence**). Any related SAE during the long-term follow-up period from 1 year to 3 years post-implantation must be reported by the investigator to Humacyte or designee immediately (**no later than 24 hours after learning of its occurrence**). Events of special interest should follow the same reporting time frame as SAEs.

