### **9.6.2 Monitoring and Reporting of Serious Adverse Events Not Related to the HAV**

Patients with ESRD have significant co-morbidities and typically experience many SAEs related to those co-morbidities that are not related to the HAV. Investigators will be asked, as part of their reporting, to identify whether a particular SAE is HAV-related.

For those events identified as not being related to the HAV, Humacyte will monitor these events for any increase in frequency that may indicate a link to the HAV. Occurrences of non-HAV related SAEs will be excluded from expedited reporting to the applicable regulatory authorities and to IECs. If aggregate analysis of these events indicates they occur more frequently with the HAV than expected, an expedited safety report may be submitted.

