3: If adequate vessel mapping has been undertaken within the 8 weeks prior to the start of Screening and there has been no significant change in the condition of the subject (including insertion of CVC) then repeat vessel mapping is at the discretion of the Principal Investigator. Vessel mapping performed by ultrasound in the clinic by the investigator is acceptable.

4: After review by the Principal Investigator, the subject's Screening eCRFs will be provided to the Medical Monitor for review and confirmation of eligibility prior to implantation.

5: Labs include hematology and chemistry. Screening labs will also include INR (or PT if INR value not available) and a serum or urine pregnancy dipstick test for women of childbearing potential. Standard of care laboratory evaluations conducted prior to consent may be used for determination of eligibility provided they are within the screening period time window.

6: Intraoperatively or immediately post-surgery and at Day 7-15, the investigator should use his/her preferred method to confirm patency and adequate flow in the HAV. At all other timepoints, duplex ultrasound will be used to assess patency, diameter of the lumen mid-conduit and flow rate and to monitor aneurysm development. After Month 12, a duplex ultrasound is to be performed at Month 24 and 36.

7: Beginning on Day 28, the investigator may evaluate the HAV to determine if it is suitable to be used for dialysis.

8: Only SAEs related to the screening procedures will be reported during the Screening period. All AEs will be reported from Day 0 after implantation up to the Month 12 visit. After the Month 12 visit up to Month 36, only the following will be reported by the investigator:

- All SAEs considered related to the HAV
- All Events of Special Interest.

9: Subjects will be assessed at a study visit that can occur anytime from Day 7 to 15.

10: Subjects withdrawn prior to the Month 36 visit will have ET assessments performed. Patients withdrawn prior to Month 12 should complete an ET that correlates with the procedures at Month 12. Patients withdrawn after Month 12 and prior to Month 36 should complete an ET visit that correlates with procedures post Month 12 through Month 36.

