## **5. STUDY SUBJECTS**

### **5.1 Disposition of Subjects**

A table of frequency counts and percentages of all enrolled subjects will be provided for the ITT set. Subject completion status and reasons for study discontinuation will be tabulated. A by-subject listing will be provided.

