#### **7.2.5 Adverse Event Summaries**

All AEs (serious and non-serious) occurring following the HAV implantation, regardless of relationship to the IMP, will be included and classified by SOC and PT using the current MedDRA.

For TEAEs, the following will be summarized and presented for the Safety analysis set:

- i. An overall summary of TEAEs, which includes:
    - a. the number and percentage of subjects experiencing a TEAE
    - b. the number and percentage of subjects experiencing a TEAE by strongest relationship to IMP
    - c. the number and percentage of subjects experiencing a TEAE by strongest relationship to study procedure(s)
    - d. the number and percentage of subjects experiencing a treatment emergent SAE (TESAE)
    - e. the number and percentage of subjects experiencing a TEAE leading to outcome of death
  - ii. the number and percentage of subjects experiencing a TEAE by SOC and PT
  - iii. the number and percentage of subjects experiencing a TEAE by SOC, PT and the strongest relationship to IMP
  - iv. the number and percentage of subjects experiencing a TEAE by SOC, PT and the strongest relationship to study procedure(s)
  - v. the number and percentage of subjects experiencing a TESAE by SOC and PT
  - vi. the number and percentage of subjects experiencing a related TESAE by SOC and PT
  - vii. the number and percentage of subjects experiencing a TEAE leading to outcome of death
-

by SOC and PT

A subject with more than one type of TEAE in a particular SOC will be counted only once in the total of subjects experiencing TEAEs in that particular SOC. Since a subject could have more than one type of TEAE within a particular SOC, the sum of subjects experiencing different TEAEs within the SOC could appear larger than the total number of subjects experiencing TEAEs in that SOC. Similarly, a subject who has experienced a TEAE in more than one SOC will be counted only once in the total number of subjects experiencing AEs in all SOCs.

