### **7.6 Subject and Graft Status**

Summaries of subject status (alive or deceased), HAV patency/usability, and reasons for HAV abandonment will be reported by frequency counts and percentages. Listings of the subject and HAV status will be provided.

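### From Month 12 to Month 36, a death judged unrelated and not arising from an Event of Special Interest gets no SAE record, yet three other sections set no such limit

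*Protocol*

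**What the plan says.** The restriction is stated in several places:

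- Protocol 9.6: "During the long-term follow-up period from 1 year to 3 years post-implantation, only the following will be reported by the investigator". The list that follows has two items, related SAEs and Events of Special Interest. SAP 7.2 repeats it.
- Protocol 9.6.1: "Any related SAE during the long-term follow-up period from 1 year to 3 years post-implantation must be reported by the investigator". The 24-hour deadline applies to these, and Events of Special Interest follow the same time frame.
- Protocol Appendix 1, note 8, gives the scope as "All SAEs considered related to the HAV" plus Events of Special Interest. SAP Appendix A, note 8, agrees.
- Protocol 9.3 lists the Events of Special Interest. Death is not on the list.

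Three other places carry no Month 12 limit:

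- Protocol 9.6.2, on SAEs judged unrelated: "Humacyte will monitor these events for any increase in frequency that may indicate a link to the HAV".
- Protocol 13.4 makes the investigator responsible for reporting every SAE to the sponsor.
- SAP 7.2.5 tabulates "the number and percentage of subjects experiencing a TEAE leading to outcome of death", overall and by SOC and PT. The TEAE definition in SAP 7.2.1 has a start but no end date, and SAP 4 plans a final analysis at 36 months.

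Death is also recorded outside the adverse event system. SAP 7.6: "Summaries of subject status (alive or deceased), HAV patency/usability, and reasons for HAV abandonment will be reported by frequency counts and percentages". SAP 5.1: "Subject completion status and reasons for study discontinuation will be tabulated". SAP 4.4.1 censors patency at death.

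**The concern.** Protocol 9.6.2 exists because an investigator's opinion that an SAE is unrelated may be wrong: the sponsor looks at such events in aggregate for a pattern. After Month 12 the same opinion decides whether the event is reported at all, so for late deaths the safeguard has nothing to work on.

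Long-term safety to 36 months is the secondary objective (Protocol 3.2), and Protocol 2.4 gives detection of late safety problems with the Luna product as the reason for follow-up beyond a year. The earlier dialysis studies saw "15 deaths, all after abandonment or during follow-up; none of the deaths were considered related to the presence of the HAV". If relatedness is judged the same way here, the fatal-event tables in the 36-month report would in effect stop at Month 12 without saying so. The same report would show a larger number of deaths under subject status. Over that period the DMC could count the deaths but might see no coded cause.

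**Working it through.** **Which deaths are reported**

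| Death | Months 0–12 | Months 12–36 |
|---|---|---|
| Judged related to the HAV | SAE | SAE |
| Arising from an Event of Special Interest, any relatedness | SAE | Reported, on the SAE time frame |
| Any other | SAE | Not reported as an AE or SAE; visible in status, disposition and censoring |

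Only the last cell is in question. An AE already open at Month 12 is followed up under Protocol 9.6.3, so a death from such an event could still be recorded.

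**How many deaths could fall there**

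The plan gives no expected number of deaths, so there is no figure to reproduce.

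Inputs from the documents:
- Up to 30 implanted subjects (Protocol Summary).
- 15 deaths in 60 subjects and more than 150 years of follow-up (Protocol 2.3.2.1), so the rate is 15/150 = 0.10 per patient-year. Because 150 is a floor, this is probably an upper figure.
- Secondary patency of 91% at 12 months and 77% at 24 months (same section).
- Follow-up regardless of patency to Month 12, and of patent HAVs only after that (Protocol 8.6).

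Assumptions: constant hazard λ, death independent of loss of patency, log-linear patency between time points, and 65% secondary patency at Month 36 (range 50% to 77%).

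Patency loss rates: a = ln(0.91/0.77) = 0.167 per year in year 2, and b = ln(0.77/0.65) = 0.169 in year 3.

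Patient-years at λ = 0.10:
- Year 1: 30 × (1 − e^−0.10)/0.10 = 28.5
- Year 2: 30 × e^−0.10 × 0.91 × (1 − e^−0.267)/0.267 = 21.7
- Year 3: 30 × e^−0.20 × 0.77 × (1 − e^−0.269)/0.269 = 16.6

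Expected deaths:
- To Month 12: 0.10 × 28.5 = 2.9
- After Month 12: 0.10 × (21.7 + 16.6) = 3.8
- Total 6.7; share after Month 12 = 3.8/6.7 = 57%
- Chance of at least one death after Month 12 (Poisson): 1 − e^−3.83 = 98%

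**Sensitivity**

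| Assumption | Deaths after Month 12 | Share of all deaths |
|---|---|---|
| λ = 0.05 | 2.1 | 59% |
| λ = 0.10 (base) | 3.8 | 57% |
| λ = 0.15 | 5.2 | 56% |
| λ = 0.10, 10% per year other withdrawal or transplant | 3.2 | 54% |
| λ = 0.10, first-year hazard 1.5 times higher | 3.6 | 47% |
| λ = 0.10, patency 60%, 42%, 30% at Months 12, 24, 36 | 2.1 | 43% |

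For hazards of 0.05 to 0.20 and Month 36 patency of 50% to 77%, the share stays between 53% and 60%.

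**How many of these would lack an SAE record**

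In the earlier studies 0 of 15 deaths were judged related. The one-sided 95% upper bound for the related fraction is 1 − 0.05^(1/15) = 18%. Apart from fatal Events of Special Interest, most or all late deaths could therefore go unreported as SAEs.

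**The case against.** The other side has several good points.

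- **Reduced late collection is deliberate.** The secondary safety endpoint itself (Protocol 4.2.1.2, SAP 2.2.2.1) narrows after Month 12 to HAV-associated SAEs and Events of Special Interest. On that view SAP 7.2.5 and SAP 7.6 measure different things and may differ. This stands as a defence of the choice. It does not explain why SAP 7.2.5 carries no note of the limit.
- **The routes by which the HAV would most plausibly cause death are covered.** Infection, thrombosis, rupture, aneurysm and anastomotic bleeding are Events of Special Interest, reported to Month 36 whatever the relatedness. A reader might infer that a late death is reported only if called HAV-related; the documents do not support that.
- **Deaths are not lost.** Subject status, disposition and censoring all show them, and SAP 8 sends all available safety data to the DMC. The eCRF is not among the documents, so a death page recording cause cannot be ruled out. What can be said is that neither document provides for one.
- **Protocol 9.6.2 can be read as covering reported SAEs only.** That is possible, but the section does not say that its monitoring ends at Month 12.
- **Protocol 13.4 asks for every SAE.** This makes the matter a contradiction to settle, not a proven absence of reports.

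A reader might also apply 0.10 per year to all 30 subjects through Month 36, which gives 30 × (1 − e^−0.3) = 7.8 deaths with 4.9 (63%) after Month 12, and conclude that most deaths in the study go unreported. That ignores the rule that only patent HAVs are followed after Month 12. The 15 earlier deaths also include some after abandonment, which this study would not observe after Month 12.

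**Conclusion.** The gap is real but narrower than it first looks. It concerns deaths between Months 12 and 36 that are judged unrelated and do not arise from an Event of Special Interest. For these the documents provide no coded fatal event, causality assessment or safety report, although the deaths themselves can be counted. Protocol 9.6.2, Protocol 13.4 and SAP 7.2.5 are not reconciled with the restriction.

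The size is about 3.8 expected late deaths, with 2.1 to 5.2 at 0.05 to 0.15 per year. That is roughly half or more of all observed deaths, but the claim that it is most of them depends on assumptions. The estimate rests on a rate carried over from two small studies, a constant hazard, and an assumed Month 36 patency.

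The primary objective is not touched: all AEs are reported to Month 12, so the 3- and 12-month analyses lose no deaths within their planned follow-up. The point is a worthwhile low-cost improvement to the 36-month safety objective.

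**What to change.** 1. In Protocol 9.6, 9.6.1 and Appendix 1 note 8, and in SAP 7.2 and Appendix A note 8, add to Month 12–36 reporting all deaths, with date and cause, whatever the relationship.
2. Reconcile Protocol 13.4 with 9.6, so that the investigator has one reporting rule for the late period.
3. State in Protocol 9.6.2 that frequency monitoring of other unrelated SAEs applies to Month 12 only.
4. Reconcile the death counts in SAP 7.2.5 and SAP 7.6, preferably by drawing both from the same death record.

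If the sponsor prefers not to extend reporting, the minimum is a note that the fatal TEAE tables and the 9.6.2 monitoring are complete only to Month 12.

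The cost is an amendment to protocol and SAP wording and about two to five extra SAE forms over two years. The downside is a higher reported death count, which the report should set against the mortality seen in the earlier dialysis studies.

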### 9.6.1 Reporting of Serious Adverse Events

Any SAE (as defined in [Section 9.2](#)) which occurs from Day 0 after implantation to 1 year post-implantation (Month 12 visit) or ET visit, whichever occurs earlier, whether or not causally related to the IMP, must be reported by the investigator to Humacyte or designee immediately (**no later than 24 hours after learning of its occurrence**). Any related SAE during the long-term follow-up period from 1 year to 3 years post-implantation must be reported by the investigator to Humacyte or designee immediately (**no later than 24 hours after learning of its occurrence**). Events of special interest should follow the same reporting time frame as SAEs.

#### CTI Global Safety & Pharmacovigilance

**SAE Telephone [contact]**

**SAE eFax #: Country-specific fax numbers will be provided in the study manual**

**E-mail: [[contact]](mailto:[contact])**

If there are any questions, or if clarification is needed regarding the SAE, please contact the Medical Monitor (see [Section 1](#)).

Follow-up information for the event should be sent promptly (within 7 days of the initial notification).

Full details of the SAE should be recorded on the medical records and in the eCRF.

The following minimum information is required:

- Study number,
- Subject number, gender and age,
- The date of report,
- A description of the SAE (event, seriousness of the event), and
- Causal relationship to the HAV.

Humacyte or Humacyte's designee will submit expedited safety reports to the regulatory agencies and IECs as necessary according to the timelines provided in the Safety Management Plan and will inform the investigators of such regulatory reports.

### **9.6.2 Monitoring and Reporting of Serious Adverse Events Not Related to the HAV**

Patients with ESRD have significant co-morbidities and typically experience many SAEs related to those co-morbidities that are not related to the HAV. Investigators will be asked, as part of their reporting, to identify whether a particular SAE is HAV-related.

For those events identified as not being related to the HAV, Humacyte will monitor these events for any increase in frequency that may indicate a link to the HAV. Occurrences of non-HAV related SAEs will be excluded from expedited reporting to the applicable regulatory authorities and to IECs. If aggregate analysis of these events indicates they occur more frequently with the HAV than expected, an expedited safety report may be submitted.

### **9.6.3 Follow-Up of Adverse Events**

If any AEs are present when a subject completes 1 year post-implantation or ET, if earlier, or if a subject is withdrawn from the study, the subject will be re-evaluated within an appropriate period of time. At the investigator's discretion, minor AEs can be re-evaluated via telephone and documented. If the AE has still not resolved, additional follow-up will be performed as appropriate. Every effort should be made by the investigator or delegate to contact the subject until the AE has resolved or stabilized or the medical monitor and investigator agree that further follow-up is not necessary. This should be documented in the subject's medical records.

## **9.7 Reporting of Pregnancy**

If a study participant becomes pregnant during study participation, basic information about the pregnancy will be recorded in the Pregnancy eCRF and submitted to Safety. If there are complications during the pregnancy, the complications are recorded as AEs. The participant will be asked to report the outcome of the pregnancy and the site should submit the information to Safety within 30 days after the outcome of the pregnancy. If there is a congenital anomaly in the infant, this will be recorded as a SAE in the data forms for the mother (i.e., the study participant).

Partner pregnancies do not need to be reported.

## **9.8 Study Suspension and Stopping Criteria**

All SAEs that may indicate acute HAV infection (<30 days post-implant), mechanical failure of the HAV, or inflammatory/immune response to the HAV will be notified within 72 hours to the DMC chair who will consider whether a formal review of study continuation should be undertaken. The DMC chair will respond to Humacyte regarding the need for a safety review within 48 hours. If such a review is deemed necessary by the DMC chair recruitment into the study will be placed on hold until that review is complete. The sites will be notified by fax or e-mail of any such hold on recruitment.

## **9.9 Data Monitoring Committee**

An independent Data Monitoring Committee (DMC) will be established to review safety on an ongoing basis and to provide recommendations about stopping, continuing or otherwise modifying the study. The DMC will consist of individuals who are not directly involved in the conduct of the study. The DMC will review data from this study on an ongoing basis with the 1st scheduled DMC review after the last patient completes Month 3 and every 6 months thereafter. A separate charter will be established that will describe the roles and responsibilities of the DMC. Responsibilities of the DMC will include review of aggregate safety data from other studies in the HAV clinical development program.

## **9.10 New Information Affecting the Conduct of the Study**

When new information becomes available for conducting the clinical study properly, Humacyte or designee will inform all investigators involved in the clinical study as well as the regulatory authorities and IECs.

# **10. STATISTICAL CONSIDERATIONS**

This is a prospective, two center, open label, single arm study with no formal hypothesis testing. Data will be summarized using descriptive statistics only.

All available data will be summarized and reported in a Clinical Study Report (CSR) when the last patient completes 3 months of follow up. A second analysis will be conducted when all patients have completed 12 months of follow up. The final analysis will occur when the final patient completes 36 months of follow up. Details of data handling and planned descriptive statistics are in the Statistical Analysis Plan.

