## Protocol Summary

Full Title	A Phase 2 Assessment of Humacyte's Human Acellular Vessel in Patients Needing Vascular Access for Dialysis
Clinical Trial Phase	Phase 2
Sponsor	Humacyte, Inc.
Planned Study Sites	2 sites in Poland
Sample Size	Up to 30 patients implanted with a Human Acellular Vessel (HAV)
Expected Enrollment Start	2Q 2019
Study Rationale	Previous studies with the HAV have used Investigational Medicinal Product (IMP) manufactured using small-scale systems (Aura and Terra). Prior to commercialisation, manufacturing has been switched to a larger-scale automated process with greater in-process controls (Luna). Based on a large number of preclinical parameters, including those used for batch release, the IMP manufactured using the Luna system is comparable to that used in earlier clinical studies. This study will allow confirmation of the short-term safety, efficacy and absence of immunogenicity of the Luna product.
Study Population	Subjects with end-stage renal disease (ESRD) who require hemodialysis and are targeted for implantation of an arteriovenous (AV) graft for dialysis access.
Enrollment Period	2 months
Study Duration	Each subject will be followed by study specific visits until he/she completes 1 year (12 months) of follow-up after implantation (irrespective of patency status). After 1 year, only subjects with a patent HAV will be followed (while the HAV remains patent) for up to 3 years (36 months) post-implantation at study visits every 6 months. The expected duration of the clinical investigation is 41 months (initiation of enrollment through completion of data collection).
Study Design	Prospective, two center, open-label, single-arm study.
Intervention Description	The IMP is Humacyte's HAV, which is a tissue-engineered vascular conduit for hemodialysis access. HAVs for this study will be manufactured using the Luna commercial manufacturing system.  Subjects will be implanted with an HAV in the forearm or upper arm

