### 4.2 Study Endpoints

#### 4.2.1 Safety Endpoints

##### 4.2.1.1 Primary Safety Endpoints – assessed at 3 months post implantation

- Adverse events indicating possible mechanical failure or weakness of the HAV
  - Anastomotic rupture
  - Anastomotic bleeding
  - Spontaneous HAV rupture
  - Aneurysm
  - Pseudoaneurysm
  - Abnormal post cannulation hemostasis
- HAV infections
- Change from baseline of PRA and anti-HAV IgG levels (at 2 months)
- All AEs/SAEs and adverse events of special interest.

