## **12. REPORTING**

Following completion of follow-up of all subjects to the 3-month endpoint, a CSR will be generated, including a summary of all available data, statistical measures, tabulated results, graphical results and interpretations. This report will be submitted to regulatory authorities in a timely manner. Addenda to the report will be generated and submitted to regulatory authorities that will include data up to 12 months, and then up to 36 months follow-up or based on timing otherwise to be defined.

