#### **4. GENERAL CONSIDERATIONS FOR DATA ANALYSIS**

CTI Clinical Trial and Consulting Services will perform all efficacy and safety statistical analyses described in this SAP. Any change to the data analysis methods described in the protocol will require an amendment of this SAP only if it changes a principal feature of the protocol. Any other change to the data analysis methods that are described in the protocol, and the justification for making the change, will be described in the clinical study report. Additional exploratory analyses of the data will be conducted as deemed appropriate.

The analyses for this study will be performed as follows:

- The primary analysis will be performed after the last subject completes 3 months of follow-up.
- A second analysis will be performed after all subjects have completed 12 months of follow-up.
- A final analysis will be performed after the last subject completes 36 months of follow-up.
- Interim safety data will be provided periodically to the Data Monitoring Committed (DMC) as per the DMC Charter.

A soft database lock will be required for the data included in the planned primary (3 months) and second (12 months) analyses. A final hard lock will be required for the final analysis at 36 months.

Statistical analyses will be primarily descriptive in nature. Unless otherwise specified, continuous variables will be summarized by presenting the number of non-missing observations, mean, standard deviation, median, inter-quartile range, minimum and maximum. Categorical variables will be summarized by presenting the number of subjects and percentage for each category.

All tabulations will be based on pooled data across centers.

Analyses will be performed using SAS for Windows statistical software, version 9.4 or higher (SAS, Cary, NC), except where other software may be deemed more appropriate.

Subject data will be listed and sorted by subject number.

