## **9. SAMPLE SIZE DETERMINATION**

This is an exploratory study with no formal hypothesis testing. No formal sample size estimates were performed. The number of subjects planned for this study is consistent with trials of this design and objectives.

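### The 3-month safety tables set no per-subject Month 3 limit on event onset, so their crude percentages would cover about 3 to 5 months of unequal follow-up

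*Protocol*

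**What the plan says.** Protocol 4.2.1.1 heads its list "Primary Safety Endpoints – assessed at 3 months post implantation", and SAP 2.2.1.1 uses the same heading. The list covers mechanical-failure events, HAV infections, PRA and anti-HAV IgG change at 2 months, and all adverse events.

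The data entering the report are defined by calendar. Protocol 10 says "All available data will be summarized and reported in a Clinical Study Report (CSR) when the last patient completes 3 months of follow up", and Protocol 12 repeats the scope: "a CSR will be generated, including a summary of all available data". SAP 4 gives the same trigger, "The primary analysis will be performed after the last subject completes 3 months of follow-up", with a soft lock, but states no day limit per subject. SAP 7.2.1 says when an event starts to count as treatment-emergent and gives no end.

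The tables are mostly crude. SAP 7.2.5 plans "the number and percentage of subjects experiencing a TEAE by SOC and PT", with similar counts for serious, related and fatal events. SAP 7.2.6 gives number and percent for spontaneous rupture, anastomotic bleeding and anastomotic rupture, with severity and time to first event but no person-time rate.

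**The concern.** The primary and secondary safety lists name the same mechanical-failure events and infections; the time window is what separates them (Protocol 4.2.1.1 and 4.2.1.2). If the tables are built as written, an event in Month 4 or 5 of an early-enrolled subject enters the 3-month percentage, while late-enrolled subjects had no such time at risk. The percentage then describes no fixed period, and it changes with how fast the sites enroll.

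The study tests no hypothesis, so these descriptive percentages are themselves the primary safety result for the Luna product.

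**Working it through.** The plan gives no expected event rate, and SAP 9 says of the sample size: "No formal sample size estimates were performed". There is therefore no planned figure to reproduce.

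**Inputs.** From the Protocol Summary: enrollment period A = 2 months and up to 30 implanted subjects. From Protocol 8.5.1: Month 3 window ±7 days and Month 6 window ±14 days. Assumptions: uniform accrual, constant hazard from implantation, complete capture of events, no early termination, 30.44 days per month.

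**Consistency of the 2 months.** 2 (enrollment) + 36 (follow-up) + 1 (last visit window) + 45/30.44 (screening) = 40.5 months, in line with the stated durations of 41 months (Protocol Summary) and 40 months (Protocol 4.3).

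**Follow-up at the cut.** It runs from 3 to 3 + A months, so 3 to 5 months with mean 4. Person-time for 30 subjects is 30 × 4/12 = 10.0 patient-years, against 30 × 3/12 = 7.5 with a Month 3 cut. The ratio is 1.33.

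**Expected crude percentage.** For true 3-month risk p, a subject followed f months has risk 1 − (1 − p)^(f/3). The table's expected percentage is the mean of this over f from 3 to 3 + A. For p = 10% and A = 2, λ = −ln(0.9)/3 = 0.03512, and the mean is 1 − (0.9 − 0.9^(5/3))/(2λ) = 1 − (0.90000 − 0.83895)/0.07024 = 13.1%. The first subject has 1 − 0.9^(5/3) = 16.1% and the last 10%.

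| True 3-month risk | A = 1 month | A = 2 (plan) | A = 4 months |
|---|---|---|---|
| 5% | 5.8% | 6.6% | 8.2% |
| 10% | 11.6% | 13.1% | 16.0% |
| 20% | 22.9% | 25.7% | 30.8% |
| 40% | 44.8% | 49.1% | 56.4% |

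At 10% and the planned accrual, that is 3.9 expected subjects of 30 instead of 3.0.

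**Capture in the extra time.** The Month 3 window closes at (3 × 30.44 + 7)/30.44 = 3.23 months, and the Month 6 window opens at (6 × 30.44 − 14)/30.44 = 5.54 months. No scheduled visit falls between them. Under the plan, nobody reaches Month 6 before the cut.

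**Which measures are exposed.**

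| Measure | Effect of unequal follow-up |
|---|---|
| TEAE and TESAE percentages (SAP 7.2.5) | Affected, no rate given |
| Spontaneous rupture, anastomotic bleeding, anastomotic rupture (SAP 7.2.6) | Affected, no rate given |
| Abnormal post-cannulation hemostasis | No entry in SAP 7.2.6, so seen only in the crude TEAE tables |
| Thrombosis, stenosis, aneurysm, pseudo-aneurysm | Percentage affected, rate per 100 person-years beside it |
| HAV infection (SAP 7.2.6) | Planned as a person-year rate |
| PRA and anti-HAV IgG | Tied to the Month 2 visit, not affected |
| Kaplan-Meier patency (SAP 6.1) | Estimates not biased by staggered entry; censored/not-censored counts do depend on the cut |

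SAP 6.1 gives no time for its event-free proportion, and SAP 6.2 lists 6, 12, 24 and 36 months, so Month 3 is not named.

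**The case against.** The best reply is that the endpoint heading already fixes 3 months, and that the words about available data describe the scope of the report without redefining the endpoint. On that reading only a table filter is unstated. This is fair as to intent, and a reader who infers that the plan deliberately counts Month 4 and 5 events as primary outcomes goes further than the text. But nothing in the SAP supplies the filter, and a programmer following it would not apply one.

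The SAP also offers real mitigation: person-year rates for five event types, and exposure reported at each analysis (SAP 7.1). That stands for those events. It does not cover the TEAE tables or the rupture and anastomotic events, and a pooled rate is not a 3-month risk.

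The size may be small. With no scheduled visit in the extra time, non-serious events and imaging-detected aneurysms would be incompletely captured; mainly serious events and events of special interest would enter, through expedited reporting. Perioperative hazards such as anastomotic bleeding would be expected to fall with time. An exact 95% interval for 3 of 30 runs from roughly 2% to 27%, far wider than the shift. The study is exploratory with no threshold, and the effect is to show more events, not fewer. All of this limits the size; none of it supplies the missing rule.

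Three stronger readings are tempting and not supported:

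- **That all primary endpoints are distorted.** The antibody endpoints and Kaplan-Meier estimates are not.
- **That the 3-month figures could not be reproduced later.** SAP 7.2.5 lists every event with its onset date and day, so either cut can be reapplied to a later database.
- **That time at risk after cannulation rises by about 48%.** The ratio (121.8 − 28)/(91.3 − 28) = 1.48 assumes every subject is cannulated on Day 28. Protocol 8.4.8 gives that only as the usual earliest day and allows for a vessel that is not yet ready.

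**Conclusion.** The concern holds in a limited form. The primary safety window is 3 months per subject, but the planned tables have no matching limit on event onset. The crude TEAE/TESAE percentages and those for rupture and the anastomotic events would therefore mix 3 to 5 months of follow-up and depend on accrual speed. Thrombosis, stenosis, aneurysm and pseudo-aneurysm percentages are affected too, with person-year rates as partial relief.

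At the planned accrual, a 10% risk would be reported somewhere between 10% (nothing captured in the extra time) and about 13% (uniform accrual, constant hazard, full capture). The 13% is probably an upper figure; slower enrollment would raise it, to 16.0% at 4 months. For events that can occur only after cannulation, the constant-hazard model does not fit well, and the documents give no first-cannulation times from which to size the effect. No type I error or power is involved. The change is worth making because it is cheap and settles what the primary percentages mean.

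**What to change.** In SAP 7.2.5 and 7.2.6, limit the primary safety tables to events with onset on or before each subject's Month 3 visit, or a fixed nominal Month 3 day if that visit is missed. A single Day 91 cut for everyone would sit badly with the ±7-day window, since the last subject may complete Month 3, and trigger the analysis, near Day 84 (91 − 7).

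Apply the same limit to the event counts in SAP 6.1, and name Month 3 there as a Kaplan-Meier estimate time. State the number of subjects followed to that point. Keep all data to the cut-off in a separate supplementary table, which still meets Protocol 10 and 12.

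The cost is some SAP wording, one onset-date filter and one extra set of tables. No new data are needed. The trade-off is that later events move out of the primary tables, so the supplementary table should appear in the same report.
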